14.2. Efficacy analyses

14.2.1. Primary efficacy analyses

Table 15. Inflammatory lesions: % change from baseline at week 12 (ITT/LOCF)

	IVM + Doxycycline	IVM + Vehicle	p-value (1)
Week 12 (ITT/LOCF)			XXX
N			
Mean ±SD			
Median			
Min,Max			
Week 12 (PP)			XXX

⁽¹⁾ p-value of CMH test based on ridit scores stratified by analysis-center.

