The approval of Ivermectin 1% cream (FDA, 2015) for the treatment of the inflammatory lesions of rosacea was based upon two identically-designed large vehicle-controlled Phase 3 randomized trials that demonstrated efficacy and safety in adults with moderate to severe papulopustular rosacea on a 12-week treatment period. In both studies, a greater proportion of subjects in the IVM 1% group achieved treatment success. Ivermectin was superior to vehicle in terms of reduction from baseline in inflammatory lesion counts (76% and 75% versus 50% for both vehicle groups, respectively)^{1.13}. For Doxycycline the two placebocontrolled pivotal phase 3 trials evaluated the efficacy and safety of doxycycline 40 mg modified release (MR) once daily versus placebo in participants with moderate to severe rosacea. These participants had 10 to 40 papules and pustules and moderate to severe erythema and telangiectasia. Both studies showed marked reductions in the number of inflammatory lesions compared with placebo. Treatment with doxycycline 40 mg MR significantly reduced the number of lesions from the first follow-up assessment at 3 weeks throughout the entire 16-week study compared with placebo (P≤ 0.005). Study by Sanchez et al. 1.14 using doxycycline with metronidazole versus metronidazole alone did demonstrate in moderate to severe rosacea that adjunctive use of sub-antimicrobial dose doxycycline significantly reduced the clinical signs of rosacea compared with metronidazole alone 1.6. Based on the complementary mechanism of action of doxycycline MR and ivermectin^{1.10}, a scientific rationale to assess the combined therapy targeting inflammatory lesions in severe rosacea is planned. Topical ivermectin cream is a promising first-line treatment to target the inflammatory lesions of rosacea, which can be used in combination with systemic doxycycline modified-release as per the recent Canadian Rosacea guideline 1.15 to provide an optimal treatment approach considering all inflammatory pathways involved in rosacea with inflammatory lesions.

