4.2.1 Inclusion criteria

In order to be eligible for the clinical trial, the subject must meet all of the following inclusion criteria:

- Male or female subject age ≥ 18 years or older;
- 2. Subject with a minimum of 20 but not more than 70 inflammatory lesions (papules and pustules) of rosacea on the face at Baseline visit;
- 3. Subject with severe rosacea with papulopustular lesions (according to the Investigator's Global Assessment, IGA score rated 4);
- 4. Female Subject of childbearing potential must have a negative urinary pregnancy test (UPT) at baseline visit (UPT should have a sensitivity of 25 IU/L or less). They must agree to use/continue a highly effective and approved contraceptive method(s) for the duration of the study and at least 4 weeks after the last study drug(s) use. A highly effective method of contraception being defined as:
 - bilateral tubal ligation;
 - combined oral contraceptives (estrogens and progesterone) or implanted or injectable contraceptives with a stable dose for at least 1 month prior to Baseline visit:
 - hormonal intra-uterine device (IUD) inserted at least 1 month prior to Baseline visit;
 - vasectomized partner for at least 3 months prior to Baseline

OR

Protocol N° RD.03.SPR.113322

version Final dated 10-FEB-2017

Page 33 of 106 CONFIDENTIAL

- 5. Is of non-childbearing potential, defined as post-menopausal (absence of menstrual bleeding for one year prior to clinical trial entry without any other medical reasons), hysterectomy or bilateral oophorectomy prior to clinical trial entry.
- 6. Willing and able to comply with all of the time commitments and procedural requirements of the clinical trial protocol. In particular, subject must adhere to the visit schedule, concomitant therapy prohibitions, and must be compliant with the treatment at study visits.
- 7. Understand and sign an Informed Consent Form (ICF) and photo consent (when appropriate) at screening, prior to any investigational procedures being performed.
- 8. Apprised of the Health Insurance Portability and Accountability Act (HIPAA), if in the US, or the Personal Information Protection and Electronic Documents Act (PIPEDA) if in Canada [or the equivalent in other regions] and is willing to share personal information and data, as verified by signing a written authorization at the screening/baseline.

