5. INVESTIGATIONAL PLAN

5.1 OVERALL CLINICAL TRIAL DESIGN

This clinical trial will be conducted as a multi-center, randomized, investigator-blind, controlled and parallel-group study in subjects with severe rosacea characterized by persistent diffuse facial erythema and inflammatory lesions (papules and pustules), and meeting other specific eligibility criteria.

A total of 270 subjects will be enrolled (ie: 135 in each group) in approximately 50 sites in the USA, Canada and Europe. Approximately 5 subjects are planned from each site.

Subjects will be enrolled at baseline and treated for 12 weeks with either Ivermectin 1% cream associated with Doxycycline 40 mg MR (CD2475-101) capsules or Ivermectin 1% cream associated with CD2475-101 placebo capsules.

There will be two parallel groups, randomized in a ratio of [1:1].

There will be up to 5 trial visits: at baseline, Screening/Baseline, Week 4 (±3 days), Week 8 (±3 days), and Week 12 (±5 days).

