3.2 SAMPLE SIZE CONSIDERATION

3.2.1 Historical data and assumptions

No previous study exists associating Ivermectin 1% cream and Doxycycline MR. Therefore, this sample size was calculated using the results of previous studies on subjects treated with Ivermectin 1% cream alone and Doxycycline MR alone.

With Ivermectin 1% cream alone, for % change from baseline in inflammatory lesion counts at week 12, results showed a standard deviation (SD) between 25.4% to 39.9% with a mean around 35%.

With Doxycycline MR alone, results showed a minimum difference of 26% at Week 12 versus Placebo.

Using this historical data, we assumed that the difference between the association (Ivermectin + Doxy) and (Ivermectin + Placebo) was at least of 15% with a SD of 35%.

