4.1.2 Secondary efficacy variables

- ▶ Percent change from Baseline in IL count at each intermediate visit: (week 4 and week 8).
- Percent of subject clear inflammatory lesions at each post-baseline visit: % of subject with 100% reduction of IL.
- ➤ Clinical Erythema Assessment (CEA) at each visit: % of subject across score. The evaluator assessed the subject's diffuse persistent facial erythema of rosacea by performing a static ("snap shot") evaluation of erythema severity at a social distance of approximately 50 cm using CEA, at each visit.

Grade	Score	Description
Clear	0	Clear skin with no signs of erythema
Almost Clear	1	Almost clear; slight redness
Mild	2	Mild erythema; definite redness
Moderate	3	Moderate erythema; marked redness
Severe	4	Severe erythema; fiery redness

Investigator's Global Assessment (IGA) at each post-baseline visit: % of subject across score. The evaluator assessed the subject's rosacea at each visit by performing a static ("snap-shot") evaluation at a social distance of approximately 50 cm, using IGA score. No reference to previous visits was to be made.

Grade	Score	Clinical Description	
Clear	0	No inflammatory lesions present, no erythema	
Almost Clear	1	ery few small papules/pustules, very mild erythema present	
Mild	2	Few small papules/pustules, mild erythema,	
Moderate	3	Several small or large papules/pustules, moderate erythema,	
Severe	4	Numerous small and/or large papules/pustules, severe erythema,	

> Stinging/Burning at each post-baseline visit: % of subject across score. The evaluator recorded the severity of subject's facial stinging/burning sensation (a prickling pain sensation) during the last 24h at each visit.

None	0	No stinging/burning		
Mild	1	ht warm, tingling/stinging sensation; not really bothersome		
Moderate	2	Definite warm, tingling/stinging sensation that is somewhat bothersome		
Severe	3	Hot, tingling/stinging sensation that has caused definite discomfort		

> Subject's Global Improvement in Rosacea at week 12/early termination visit: % of subject across score. The subject evaluated his/her improvement in rosacea at last visit compared with his/her rosacea condition before the study

Complete Improvement	0	All signs and symptoms of disease have resolved (100% improvement from Baseline)
Excellent Improvement	1	Nearly all signs and symptoms cleared (90% improvement from Baseline)

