6.1 DATA PRESENTATION

All continuous data will be summarized at each visit using usual statistics: number of values, mean, median, standard deviation, minimum and maximum, and by frequency distribution (n, %) for qualitative data. For ordinal data, both frequency distribution and usual statistics will be presented. All tables will be presented by parallel group and by visit (when applicable).

The adverse events will be descriptively summarized (n, %). All summaries are based on the safety population (APT). The adverse events will be descriptively summarized (n, %) by relationship to study treatments within System Organ Class (SOC) and preferred term (MedDRA). Subjects will be descriptively summarized (n, %) by intensity (*i.e.* mild, moderate and severe) of adverse event, SOC and preferred term. Deaths and serious adverse events will be reported as well as withdrawals due to adverse events. A subject will be counted once per System Organ Class (SOC) and once per preferred term even if more than one occurrence of an event was reported within a SOC or preferred term. In the summary by categories of intensity, the adverse event with the highest intensity will be used. The subject will be counted once per SOC (highest intensity whatever the AE within the SOC) and once per preferred term (highest intensity whatever the AE within the preferred term).

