6.3 EFFICACY ANALYSES

6.3.1 Primary efficacy analyses

The primary objective of this study was to demonstrate the superiority of the IVM/Doxy compared to IVM/Placebo, in terms of percent change from baseline in inflammatory lesion count at week 12.

The primary efficacy endpoint will be analyzed by using the Cochran-Mantel-Haenszel (CMH, FREQ procedure from SAS®) statistic, stratified by center (or analysis-center) after ridit transformation with the row mean difference statistics, testing the hypothesis of equality on ITT/LOCF population. PP analysis will also be performed to assess the robustness of the results obtained on ITT/LOCF population. The p-values will have to be inferior to 0.05 at week 12.

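### The plan pre-specifies no between-arm estimate or confidence interval for the primary endpoint, and five non-primary outcomes are tested without their recorded baselines

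*SAP*

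**What the plan says.** **Primary endpoint.** SAP 6.3.1, protocol 9.1.4 and the synopsis define the primary analysis as a centre-stratified CMH row-mean-score test on ridits, "testing the hypothesis of equality on ITT/LOCF population", with success at p<0.05. SAP 6.1 sets the general reporting rule: "All continuous data will be summarized at each visit using usual statistics: number of values, mean, median, standard deviation, minimum and maximum". Table 15 follows it, with N, mean ± SD, median and range per arm for ITT/LOCF, a PP row, and a column headed by the "p-value of CMH test based on ridit scores stratified by analysis-center". It has no column for a difference or an interval. SAP section 7 adds only the full-clearance endpoint.

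**Sizing.** SAP 3.2.1 and protocol 9.2.1 assume that the difference between arms "was at least of 15% with a SD of 35" percent.

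**Other outcomes.** The protocol 5.4 flow chart records CEA, stinging/burning, ocular signs, EQ-5D-5L and WPAI:GH at Visit 1. Tables 19, 21, 23, 33 and 35 test each on post-baseline or last-visit values only, stratified by analysis-centre. For CEA, stinging/burning and ocular signs this matches the protocol endpoint definition, the percentage of subjects across scores.

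**The concern.** The trial was justified by a difference in mean percent change, but the planned test works on ranks and returns nothing on that scale. A reader of the results would have a p-value and two sets of descriptives, with no stated answer to how large the benefit is and how precisely it is known.

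On this endpoint the choice of summary is not neutral. Percent change cannot fall below -100%. Protocol 2.1 gives lesion reductions on ivermectin cream of "76% and 75% versus 50% for both vehicle groups, respectively", so the control arm is expected well down towards that floor. The SAP also adds an endpoint for the percentage "of subject with 100% reduction of IL", so ties at -100% are expected. In such data, differences in means, differences in medians and rank-based shifts measure different things.

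For the five raw-score outcomes, leaving out the baseline leaves chance baseline differences in the comparison as avoidable noise.

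**Working it through.** **1. The plan's own figure.** n per arm = 2 × [35 × (1.960 + 1.282) / 15]² = 114.4, against 114 stated. Power at 114 is 89.9%. Then 114 / 0.85 = 134.1, giving 135 per arm. The sample size reproduces and is not in question. It confirms that the planning quantity is a difference in means.

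**2. Precision that could be reported.** Half-width of a 95% CI = t(0.975, 268) × SD × √(2/135), over the documents' SD range:

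| SD | Half-width (points) |
|---|---|
| 25.4 | 6.1 |
| 35 | 8.4 |
| 39.9 | 9.6 |

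This assumes equal SDs, which the floor makes doubtful. On the range -100 to 0, the largest possible SD is √(75 × 25) = 43.3 at a mean of -75%, but √(90 × 10) = 30 at a mean of -90%. More spread than that needs subjects who end above baseline. Hence a heteroscedasticity-robust standard error.

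**3. Do the estimators agree?** Simulation assumptions:
- Baseline counts are uniform over 20-70, from the entry criterion of "a minimum of 20 but not more than 70 inflammatory lesions".
- Follow-up counts are gamma-Poisson.
- The control mean is -75% and the true mean difference is 15 points.

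Over control SDs of about 26 to 40, the difference in means averages 15, the difference in medians about 5-11, and the Hodges-Lehmann shift about 3-9. Only the first is the sizing quantity.

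**4. How would a mean-difference CI behave beside the CMH test?** Same model, 27 analysis-centres with 5 + 5 subjects, 3,000 runs, linear model with treatment and centre, HC3 standard error:

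| True difference | Control SD | Coverage | Half-width | CMH power | CI and CMH disagree | of which only the CI excludes 0 |
|---|---|---|---|---|---|---|
| 15 | 26.8 | 0.955 | 5.2 | 1.000 | 0% | 0% |
| 15 | 35.8 | 0.953 | 6.9 | 0.974 | 2.6% | 2.6% |
| 15 | 40.8 | 0.955 | 7.8 | 0.898 | 9.7% | 9.5% |
| 10 | 36 | 0.958 | – | – | 25.2% | 22.4% |

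At 10 points the disagreement is about 25-30% over SD 35-40. With no effect it is 4.3% at SD 27 and 4.9% at SD 36. With 30 unbalanced centres of 4-22 subjects and centre effects, coverage is 0.939-0.967. A centre-stratified Mann-Whitney probability disagrees with the CMH test in 0-3% of trials. No run included dropout or LOCF.

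**5. Baseline adjustment of the raw-score outcomes.** The documents give no baseline-to-follow-up correlation, so r is assumed. Stratified rank ANCOVA, 27 centres of 10, latent shift 0.35 SD, 2,000 runs; power shown:

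| Outcome shape (assumed) | r 0.3: raw → pooled slope | r 0.6: raw → pooled slope |
|---|---|---|
| Four-level | 0.731 → 0.754 | 0.736 → 0.863 |
| Stinging-like | 0.661 → 0.685 | 0.680 → 0.785 |
| Two-level baseline, 20/80 | 0.714 → 0.728 | 0.733 → 0.805 |
| Ocular-like | 0.563 → 0.588 | 0.567 → 0.656 |
| EQ-item-like | 0.577 → 0.589 | 0.547 → 0.641 |
| Continuous | 0.756 → 0.776 | 0.757 → 0.894 |

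The loss at r = 0 is negligible. Null rejection is 0.037-0.057 raw and 0.042-0.059 adjusted. A separate slope in each centre costs 1.1-4.0 power points at r 0.3. Sites are small ("Approximately 5 subjects are planned from each site"), so the slope must be pooled. IGA is not counted because eligibility fixes its baseline at 4. DLQI is not counted because Table 31 also tests percent change.

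**The case against.** **The difference can be read off Table 15.** True in part. Subtracting the means gives the sizing quantity, and the SDs and Ns give a crude interval. But the same table also offers the medians, the crude interval ignores the centre stratification, and neither is pre-specified.

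**A reader might infer that the effect size could be quietly picked after unblinding.** The documents do not support that. Protocol 9.1.4 requires analysis changes decided after database lock to be justified and documented, and protocol 9.1 requires changes to the final SAP to be documented in the trial report. A late choice would be visible. The gap is that no choice has been made in advance.

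**The 75-76% may not be a mean.** This stands. Protocol 2.1 does not say whether it is a mean or a median, and it comes from moderate to severe rosacea, whereas this trial enrols only IGA 4. If 75% is roughly a median (control mean -65%), the same 15-point difference appears as about 10-11 in medians and 8-10 as a Hodges-Lehmann shift. The estimators still diverge, but less.

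**The interval treats imputed values as observed.** This stands. SAP 5.4 carries the last value, or baseline, forward, and the coverage figures do not model this.

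**A mean-difference CI can contradict the deciding test, and a Hodges-Lehmann shift is a recognised companion to a rank test.** Both are fair. The mean difference is preferred here only because it is the quantity used for sizing. Another estimator is a legitimate choice if it is named in advance.

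**The raw-score tests follow the endpoint wording and one uniform method.** Agreed; they are valid. A reader might infer bias from the unused baselines, but randomisation rules that out. The cost is precision only.

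**Conclusion.** The point holds as a gap in reporting and precision. The primary endpoint has a pre-specified decision rule but no pre-specified estimate or interval for the 15-point mean difference on which 270 subjects were justified. It would be wrong to conclude that the superiority claim, type I error or sample size is at risk: the CMH test is fully specified and the sample size reproduces.

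The size of the estimator divergence rests on the assumed gamma-Poisson counts and control mean. The direction follows from the floor and is robust to the alternative control mean tried. The planning half-width of 6.1-9.6 points rests only on the documents' SD range and equal variances.

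The raw-score point is secondary and affects no primary result. Its gain depends on correlations the documents do not give. It is probably smallest for CEA, whose baseline shell in Table 14 lists only grades 3 and 4, and for EQ-5D-5L items if most subjects start at level 1.

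**What to change.** **Primary (SAP 6.3.1 and Table 15, ITT/LOCF and PP).**
- Keep the CMH p-value as the sole decision rule.
- Add the difference in mean percent change with a 95% CI from a linear model with treatment and analysis-centre and an HC3 standard error.
- Label it supportive. State that it treats LOCF values as observed and that it may disagree with the CMH result.
- Optionally add the centre-stratified Mann-Whitney probability with 95% CI as the estimate that matches the rank test. It needs at least two subjects per arm in each analysis-centre.
- Settle the wording before unblinding.

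**Non-primary outcomes.** For CEA, stinging/burning, ocular signs, EQ-5D-5L and the WPAI daily-activity item, replace the raw-score CMH test with stratified rank ANCOVA: CMH on ridit residuals, baseline score as covariate, one slope pooled across centres. Keep the planned test for the WPAI work items. Those items are skipped by subjects not in paid work, so requiring both values would select on post-baseline employment.

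**Cost.** SAP text and modest programming on data already collected. There are no new subjects or assessments, and no change to alpha, N or the primary test. The one real cost is a table in which the interval and the p-value may point different ways, so the text must say which one decides.

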14.2.2. Secondary efficacy analyses

14.2.2.1. Inflammatory lesions

Table 16. Inflammatory lesions: % change from baseline at other post-baseline visit (ITT/LOCF)

	IVM + Doxycycline	IVM + Vehicle	p-value (1)
Week 4 (ITT/LOCF)			XXX
N			
Mean ±SD			
Median			
Min,Max			
Week 8 (ITT/LOCF)			XXX

⁽¹⁾ p-value of CMH test based on ridit scores stratified by analysis-center.

Table 17. Inflammatory lesions: 100% reduction from baseline at each post-baseline visit (ITT/LOCF)

	IVM + Doxycycline	IVM + Vehicle	p-value (1)
Week 4 (ITT/LOCF)			XXX
N			
No (n,%)			
Yes(n,%)			
Week 8 (ITT/LOCF)			XXX
Week 12 (ITT/LOCF)			XXX

⁽¹⁾ p-value of CMH test based on ridit scores stratified by analysis-center.

Table 18. Inflammatory lesions: Count at each visit - Descriptive (ITT/LOCF)

	IVM + Doxycycline	IVM + Vehicle
Baseline		
N		
Mean ±SD		
Median		
Min,Max		
Week 12 (ITT/LOCF)		

14.2.2.2. Clinician's Erythema Assessment

Table 19. Clinician's Erythema Assessment: Raw value at each visit (ITT/LOCF)

	IVM + Doxycycline	IVM + Vehicle	p-value (1)
Baseline			NA
Week 4 (ITT/LOCF) N 0: Clear n (%) 1: Almost clear n (%) 2: Mild n (%) 3: Moderate n (%) 4: Severe n (%) Mean ±SD Median Min,Max			XXX
Week 12 (ITT/LOCF)			XXX

⁽¹⁾ p-value by CMH test based on ridit scores stratified by analysis-center.

14.2.2.3. Investigator's Global Assessment

Table 20. Investigator's Global Assessment full scale at each visit (ITT/LOCF)

	IVM + Doxycycline	IVM + Vehicle	p-value (1)
Baseline N 0: Clear n (%) 1: Almost clear n (%) 2: Mild n (%) 3: Moderate n (%) 4: Severe n (%) Mean ±SD Median Min,Max			NA
Week 12 (ITT/LOCF)			XXX

⁽¹⁾ p-value by CMH test based on ridit scores stratified by analysis-center.

14.2.2.4. Stinging/Burning severity score

Table 21. Stinging/Burning at each visit (ITT/LOCF)

	IVM + Doxycycline	IVM + Vehicle	p-value (1)
Baseline			NA
N			
0: None n (%)			
1: Mild n (%)			
2: Moderate n (%)			
3: Severe n (%)			
Mean ±SD			
Median			
Min,Max			
•••			
Week 12 (ITT/LOCF)			XXX

⁽¹⁾ p-value by CMH test based on ridit scores stratified by analysis-center.

14.2.2.5. Subject's Global Improvement

Table 22. Subject's Global Improvement at last visit (ITT)

	IVM + Doxycycline	IVM + Vehicle	p-value (1)
N			XXX
0: Complete Improvement n (%)			
1: Excellent Improvement n (%)			
2: Very good Improvement n (%)			
3: Good Improvement n (%)			
4: Minimal Improvement n (%)			
5: No Change n(%)			
6: Worse n (%)			
Mean ±SD			
Median			
Min,Max			

⁽¹⁾ p-value for between treatment difference, by CMH test based on ridit scores stratified by analysis-center.

14.2.3. Exploratory efficacy analyses

14.2.3.1. Ocular signs

Table 23. Ocular signs and symptoms at each visit (ITT)

	IVM + Doxycycline	IVM + Vehicle	p-value (1)
Baseline			NA
N			
0: None n (%)			
1: Mild n (%)			
2: Mild-Moderate n (%)			
3: Moderate-Severe n (%)			
4: Severe n (%)			
Mean ±SD			
Median			
Min,Max			
Week 12 (ITT)			XXX

⁽¹⁾ p-value by CMH test based on ridit scores stratified by analysis-center.

14.2.3.2. Flushing

Table 24. Number of flushing per week: % change from baseline (ITT)

	IVM + Doxycycline	IVM + Vehicle	p-value (1)
Week1			XXX
N			
Mean ±SD			
Median			
Min,Max			
Week 12			XXX

⁽¹⁾ p-value of CMH test based on ridit scores stratified by analysis-center.

Table 25. Number of flushing per week: Count at each visit - Descriptive (ITT)

	IVM + Doxycycline	IVM + Vehicle
Baseline		
N		
Mean ±SD		
Median		
Min,Max		
Week 12		

Table 26. Mean score severity of flushing per week: change from baseline (ITT)

	IVM + Doxycycline	IVM + Vehicle	p-value (1)
Week1 2 grades less n (%) 1 grade less n (%) 0: No change n (%) 1 grade more n (%) 2 grades more n (%)			xxx
Week 12			XXX

⁽¹⁾ p-value of CMH test based on ridit scores stratified by analysis-center.

Table 27. Mean score severity of flushing per week: Count at each visit - Descriptive (ITT)

	IVM + Doxycycline	IVM + Vehicle
Baseline		
N		
1-Mild		
2-Moderate		
3-Severe		
Mean ±SD		
Median		
Min,Max		
Week 12		

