9.1.1.1 Primary efficacy variable

The primary endpoint is the percent change from Baseline in Inflammatory Lesion count at Week 12.

9.1.1.2 Secondary efficacy variables

The secondary efficacy endpoints are:

- Percent change from Baseline in Inflammatory Lesion count at each intermediate visit
- CEA at each post-Baseline visit: % of subjects across scores
- IGA at each post-Baseline visit: % of subjects across scores
- Stinging/burning at each post-Baseline visit: % of subjects across scores
- Percent change from Baseline (medical history) in terms of flushing count per week over 12 weeks
- Change from Baseline (medical history) in terms of flushing severity score per week over 12 weeks
- Global improvement in rosacea at the last visit: % of subjects across scores

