3.2.2 Sample size calculation

With the assumptions mentioned above, a total of 114 evaluable subjects per group were to be required to demonstrate at least 15% difference at Week 12, with 90% power.

To allow a 15% rate of subjects excluded from analysis (drop out, lost to follow-up, etc.) at Week 12, 135 subjects per group (270 in total) were to be enrolled.

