6. STATISTICAL METHODS AND DATA CONSIDERATIONS

SAS version 9.3 will be used for all analyses. All tests will be two-sided and significance will be declared at a 0.05 level.

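### Flushing has no single pre-stated analysis: the SAP appears to test each diary week separately, and it moves both flushing variables from secondary to exploratory without listing the change

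*SAP*

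**What the plan says.** - **Endpoint.** Protocol 9.1.1.2 lists flushing count and flushing severity as secondary endpoints. The count is worded "Percent change from Baseline (medical history) in terms of flushing count per week over 12 weeks", and severity is worded in parallel. The protocol synopsis lists both without the reference to 12 weeks.
- **Data.** Baseline is the subject's report for the week before the visit (Protocol 7.1.6). During treatment, daily diary entries are reduced to one count and one average severity per week.
- **Classification.** SAP 4.1.3 places both variables among the exploratory ones and drops the reference to 12 weeks. SAP section 7, which lists changes from the protocol's analysis, has one entry (complete clearance of lesions) and does not mention flushing.
- **Tests.** "Table 24. Number of flushing per week: % change from baseline (ITT" and "Table 26. Mean score severity of flushing per week: change from baseline (ITT" each carry a stratified CMH p-value at Week 1 and at Week 12. Tables 25 and 27 are descriptive. SAP 6.3.2 has the non-primary efficacy variables tested at every post-baseline time. SAP section 6 states: "All tests will be two-sided and significance will be declared at a 0.05 level". Neither document gives a multiplicity rule.
- **Missing values.** SAP 5.4 confines LOCF to lesion count and IGA, so flushing is analysed as observed.

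**The concern.** The diary yields up to 12 weekly values per subject for each variable. The tables set these out as separate weekly comparisons. No week is named as the one that counts, and no mean, total or repeated-measures model combines them.

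Two things follow. The report can contain a run of weekly p-values, some below 0.05 and some not, with no rule for which one answers whether adding doxycycline reduces flushing. And each comparison rests on one week's count, although neighbouring weeks carry information on the same question.

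The unlisted move from secondary to exploratory adds to this. A reader holding the protocol expects a secondary result on flushing and is not told in SAP section 7 that its status changed.

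**Working it through.** **1. The plan's own figure.** The sample size is set "to demonstrate at least 15% difference at Week 12, with 90% power", on a difference that "was at least of 15% with a SD of 35" per cent.

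n per group = 2 × [35 × (1.960 + 1.282) / 15]² = 114.4. The plan states 114; rounding up gives 115.

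114 / 0.85 = 134.1, hence 135 enrolled per group. The calculation reproduces, but it concerns lesion counts. No rate, variance, correlation or power is given for flushing, so everything below rests on stated assumptions.

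**2. Number of tests.** Only the Week 1 and Week 12 rows are printed in Tables 24 and 26. The SAP shortens shells elsewhere: Table 20 is titled as covering each visit but prints only Baseline and Week 12. With a weekly endpoint, the natural reading is 12 count tests and 12 severity tests, 24 in all.

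**3. Chance of at least one p < 0.05 with no effect.** For 12 independent tests it is 1 − 0.95¹² = 46%; for 24 it is 1 − 0.95²⁴ = 71%. Weekly tests on the same subjects are correlated, so the table uses simulated z-statistics with an equal correlation ρ between any two weeks. The 24-test column takes count and severity as uncorrelated.

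**4. Precision.** With equal weekly variances, the variance of a k-week mean relative to one week is [1 + (k − 1)ρ] / k. At k = 12 and ρ = 0.3 this is 4.3/12 = 0.358, so one week's standard error is 1/√0.358 = 1.67 times that of the mean.

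| assumed ρ | any of 12 tests < 0.05 | any of 24 tests < 0.05 | SE, one week ÷ 12-week mean | SE, one week ÷ 4-week mean |
|---|---|---|---|---|
| 0.3 | 40% | 63% | 1.67 | 1.45 |
| 0.5 | 32% | 54% | 1.36 | 1.26 |
| 0.7 | 23% | 41% | 1.17 | 1.14 |
| 0.9 | 14% | 25% | 1.05 | 1.04 |

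If correlation instead decays with the gap between weeks, the 12-test figures are 44%, 41%, 34% and 21%.

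**5. Precision is not power.** Suppose the effect grows linearly to Week 12.

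- The 12-week mean sees 6.5/12 = 0.54 of the Week 12 effect. Its expected z is 0.90 (ρ = 0.3) down to 0.57 (ρ = 0.9) of the Week 12 test's.
- A Weeks 9–12 mean sees (9 + 10 + 11 + 12)/48 = 0.875 of it. Dividing by √[(1 + 3ρ)/4] gives 1.27, 1.11, 0.99 and 0.91 at ρ = 0.3, 0.5, 0.7 and 0.9.
- If the effect is level over Weeks 9–12, the advantage of that mean is the last column of the table.

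**6. Simulation on assumed counts.** Inputs, none of them from the documents: 135 per arm, mean about 6 flushes a week, over-dispersed, 25% reduction, weekly noise SD 0.3 (low) or 0.6 (high), and an effect either immediate or building to Week 8. Ranges cover runs with slightly different settings.

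| analysis | power, low noise | power, high noise |
|---|---|---|
| Week 12 % change, either effect shape | 49–60% | 32–43% |
| Weeks 9–12 mean, % change, either shape | 68–74% | 53–59% |
| Weeks 9–12 mean, baseline-adjusted ranks, either shape | 71–78% | 56–66% |
| 12-week mean, effect building up | 44–52% | 32–40% |

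Most of the gain comes from averaging, with a smaller part from baseline adjustment. With no effect, at least one of the 12 weekly count tests was below 0.05 in 28–35% of trials.

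**7. Severity.** Protocol 7.1.6 grades flushing as mild, moderate or severe, and Table 27 codes these 1 to 3. Table 26 allows changes of −2 to +2 only, which is the full range of a 1-to-3 scale. A week without flushing has no code, so a subject who stops flushing has no severity value to average.

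**The case against.** **Flushing is exploratory in the SAP.** No trial claim rests on it, neither document powers it, and weekly description of an exploratory outcome is ordinary. This stands and lowers the stakes. It does not supply the missing summary, and the change of status is itself unrecorded.

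**The protocol wording may not call for a period-wide test.** A reader might infer that the SAP dropped a required 12-week analysis. The documents do not support that: a weekly count over 12 weeks can equally mean weekly values followed to Week 12, which is what Table 24 shows, and the synopsis omits the phrase. Under either reading no week or summary is designated.

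**The count of 24 tests is not printed.** It is inferred from shortened shells. Read literally, the tables test Weeks 1 and 12 and leave the rest untested, again with neither week named as decisive.

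**Averaging is not always better.** A reader might infer that weekly testing throws power away at no gain. Step 5 shows that this depends on the shape of the effect and the correlation: a 12-week mean can lose to the Week 12 test, and at ρ = 0.9 the gain in standard error is only about 5%.

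**Weekly results have a purpose.** Protocol 3.2 names time to onset of action as something the study will evaluate. Weekly figures should stay, and this can be met by description.

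**Conclusion.** The point holds in a limited form. As written, the SAP gives no single pre-stated answer on flushing. It appears to give up to 12 unadjusted tests per variable, from which any one can be quoted.

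The chance of at least one count p-value below 0.05 with no effect is about 30% on the simulated inputs, and 14–44% over the correlations and patterns tried. A single week is less precise than a mean of several, by 5% to 67% in standard error against a 12-week mean for ρ from 0.9 to 0.3. The first conclusion needs no assumption about variability; the sizes do, because the documents give none for flushing.

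A reader might go further and take this as a threat to the trial's main result. It is not: the primary endpoint has one test at Week 12 and is untouched. The change is worth making because it is cheap and uses data already collected. The unlisted move from secondary to exploratory needs correcting in any case.

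**What to change.** Before unblinding, amend the SAP as follows. If unblinding has already happened, label the new summary as post hoc.

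1. **Count.** Name one test: each subject's mean weekly count over Weeks 9–12, compared by a rank analysis stratified by analysis-center and adjusted for baseline count. State the minimum number of diary weeks required, since missing values are not replaced, and how a partial last week is handled, since the Week 12 visit may fall up to five days early (Protocol 5.1). Using the mean count also keeps subjects with no baseline flushing, for whom a percent change cannot be computed.
2. **Weekly values.** Show them, together with the 12-week mean, descriptively and without p-values.
3. **Severity.** First state how a week without flushing is scored, for example as grade 0, and extend Tables 26 and 27 to match. Then name one summary in the same way. Check that severity was recorded for the last four weeks: the Week 12 steps in Protocol 5.5.3 mention frequency only, while the flow chart in 5.4 covers both.
4. **Status.** Record the move from secondary to exploratory in SAP section 7, with the reason.

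The cost is SAP wording and simpler tables, with no new data. The downside is that weekly p-values are given up, so an effect confined to the early weeks, which bears on time to onset, would be shown only descriptively.
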